11.4 Reporting Protocol Deviations

The Investigator is obligated to follow the protocol without departure from the requirements written in the protocol. If the Investigator deviates from the protocol requirements, the Sponsor will make the determination as to whether the participant will continue in the study. The Sponsor also has the right to discontinue the participant for protocol deviations / violations. All protocol deviations must be documented in the CRFs.

12.0 Ethics and Regulatory Requirements

The study will be carried out in accordance to the protocol and with principles specified in the current version of the Declaration of Helsinki, the guidelines of Good Clinical Practice, the European Directive on medical devices 93/42/EEC and the ISO Norm 14155 and ISO 14971.

12.1 Institutional Review Board / Independent Ethics Committee

The Principal Investigator will provide the IRB / IEC with all appropriate materials as required by their IRB / IEC, including but not limited to the clinical study protocol, informed consent form, and any advertising materials. The study will not be initiated until the IRB / IEC provides written approval of the aforementioned documents and until approval documents have been obtained by the Principal Investigator and Sponsor or Sponsor designee. The Investigator will not participate in the decision. If the Investigator is an IRB or IEC member, documentation must be provided indicating recusal from the approval process. Appropriate reports on the progress of this study by the Principal Investigator will be made to the IRB / IEC as required by local and applicable government regulations and in agreement with policy established by the Sponsor. The Investigator is required to maintain an accurate and complete record of all written correspondence to and received from the IRB / IEC and must agree to share all such documents and reports with the Sponsor. No changes from the final approved protocol will be initiated without the IRB / IEC's prior written approval or favorable opinion of a written amendment, except when necessary to eliminate immediate hazards to the participants or when the change involves only logistics or administration.

12.2 Investigator's Responsibilities

The Investigators are responsible for performing the study in full accordance with the specifications of this protocol and in accordance with principles consistent with Declaration of Helsinki, Good Clinical Practice and currently applicable regulations. Information regarding any study centres participating in this study that cannot comply with these standards will be documented.

12.3 Participant Informed Consent Requirements

Written and oral information about the study in a language understandable by the patient will be given to all patients by the Investigator and/or designee. Written informed consent will be obtained from each patient before any procedures or assessments that would not otherwise be required for the care of the patient are done and after the aims, methods, anticipated benefits, potential hazards, and insurance arrangements in force are explained and the patient has been given sufficient time to ask questions and consider participation in the study. It will also be explained to the patients that they are free to refuse entry into the study and free to withdraw from the study at any time without prejudice to future treatment. It is permissible for a third person (e.g., a family member) to be present during the explanation of the study.

The written Informed Consent Form (ICF) is to be in compliance with Good Clinical Practice guidelines. The Sponsor and / or designated Contract Research Organisation (CRO) will approve the ICF and all amendments to the ICF prior to submission to the IRB/IEC. A copy of the ICF to be used will be submitted by the Investigator to the IRB/IEC for review and approval prior to the start of the study. Each study site must provide the Sponsor with an unsigned copy of IRB / IEC-approved ICF along with applicable documentation to support this approval. The original signed ICF is retained in

the participant's study records, and a copy is provided to the participant. A second copy may be filed in the participant's medical record, if allowed by institutional policy.

13.0 Data Handling and Record Keeping

13.1 Recording, Collection and Transfer of Data

The primary source document for this study will be the participant's medical record. If separate research records are maintained by the Investigator(s), the medical record and the research records will be considered the source documents for the purposes of auditing the study.

Applicable source data will be manually transcribed to approved CRFs. The Investigator is ultimately responsible for the accuracy of the data transcribed on the forms. All source documents and CRFs will be completed as soon as possible after the patient's assessments have been completed.

The Principal Investigator (PI) will review CRFs to indicate that, to his / her knowledge, they are complete and accurate. If further changes are made after this, the PI will need to again sign the Investigator signature page. Designated source documents will be signed and dated by the appropriate study personnel. Investigators must agree to complete and maintain source documents and CRFs for each participant in the study.

All research data will be entered, either electronically or manually, into a computerised database. The PI will maintain a confidential list of study participants which will include each participant's study number, name, date of birth and unique hospital identification number if applicable. This list will be kept by the PI and will not be collected by Sponsor. A notation will be made in the participant's case history / medical chart that he / she is participating in a clinical study and has provided a signed and dated ICF. The PI must also maintain a separate screening log of all the patients screened for participation in the study; it should include gender; age; eligibility status; reason for ineligibility, if applicable; and study allocated participant number, if applicable.

13.2 Clinical Data Management

The Sponsor and/or designated CRO will be responsible for the processing and quality control of the data. Data management will be carried out as described in the Sponsor's or CRO's standard operating procedures (SOPs) for clinical studies. The handling of data, including data quality control, will comply with applicable regulatory guidelines and the Sponsor's SOPs as well as provisions of a study-specific Data Management Plan.

13.3 Archiving

All study documentation at the Study site and Sponsor site will be archived in accordance with Sponsor's quality standards and SOPs.

The Study site will maintain all research records, reports, and case history reports for a period of 15 years after study closure.

At the completion of the study, details of the archival process must be provided to the Sponsor. Study records are subject to inspection by applicable health and regulatory agencies at any time.

Records to be retained at the Study site include, but are not restricted to:

- Source data and the primary records upon which they are based (e.g., participant's progress notes, adverse event data, test results, and any other diagnostic procedures required to evaluate the progress of the study).
- Signed protocols and protocol amendments
- Product accountability records
- Study personnel signature log
- Monitoring logs
- Correspondence to and from the Sponsor, designee and IRB/IEC
- Principal Investigator and co-Investigator(s) Curriculum Vitae (CVs)
- Signed ICFs
- Patient screening and randomisation log
- SAE reports
- IRB / ICE approval letters and correspondence if applicable
- Other documents pertaining to the conduct of the study

These documents must be maintained and kept on file by the Study site so that the conduct of the study can be fully documented and monitored.

Appendix 1: Details of Protocol Amendments.

Change	Protocol Version No. and date	Details of changes made
1	Version 1.0 14FEB2020	New document
2	Version 2.0 25AUG2020	
Section 1.2 added to expand background information on device mechanism and function Figs 1 & 2 added illustrating device and hydrogel layers
 
Section 1.3 Rationale for testing the new formulation hydrogel expanded. More detail regarding hydrogel formulations and testing in humans added. Clarified that devices are the same they differ only by their hydrogel layer.
 
Section 2.0 Endpoints amended for clarity
 
Section 3.0 Expanded for clarification of study design, more detail added regarding patient groups and new schematic of patient journey added. Rationale for not randomising patients clarified
 
Section 3.1 More detail added to clarify why stroke acute stroke patients are to be recruited instead of using healthy volunteers
 
Section 4.0 Schedule of Events added
 
Section 5.0 Participant Completion and Withdrawal / Discontinuation added
 
Section 6.0 Study Treatments added, method for device allocation also expanded to include rationale for a non-randomised cohort observation study and not a randomised controlled study
 
Section 7.0 Description of Protocol Procedures and Assessments added. Process for obtaining informed consent expanded and assessment of eligibility added to ensure that stroke patients will only be recruited if they can give consent for themselves. Patients with impaired mental capacity will not be recruited on to the study
 
Section 8.0 Statistical Analysis and Sample Size Determination added
 
Section 9.0 Reporting of Adverse Events & Device Deficiencies added
 
Section 10.0 Source Data and Documentation added
 
Section 11.0 Quality Control and Quality Assurance added to clarify management of data
 
Section 12.0 Ethics and Regulatory Requirements added
 
Section 13.0 Data Handling and Record keeping added
 
Appendix 2 Regulatory Approval for the devices added
 
Appendix 3 Sample Case Report Forms added

Appendix 2: Regulatory Approvals.

EMEA Regulatory Clearances by Country	Clinical Indications	Reference	Date
EU/EFTA	
 – To increase blood circulation, – For the prevention of venous thrombosis – For the prevention and treatment of oedema – For promoting wound healing – For promoting healing of tendon and ligament injuries – For the treatment of venous insufficiency and ischemia 	CE Marking GB12/87339 (T3, XT-3)	Oct 2010
Saudi Arabia	
 – DVT prevention – Increasing blood circulation 	MDMA 18020263	Feb 2018
AMERICAS Regulatory Clearances by Country	Clinical Indications	Reference	Date
USA	
 – stimulation of healthy muscles in order to improve or facilitate muscle performance. 	K134001	May 2014
	
 – Increasing local blood circulation, and – Immediate post-surgical stimulation of the calf muscles to prevent venous thrombosis. – Oedema reduction – Stimulation of the calf muscles to prevent venous thrombosis in non-surgical patients at risk for venous thromboembolism 	K133638 K152667 K160299 K163125 (T-2, R-2) K180082 (T-2, R-2) K181059 (T-3) K191113 (T-2, T-3)	Aug 2014) Oct 2015 Apr 2016 Apr 2017 Feb 2018 May 2018 Sep 2019
	
 – Increasing local blood circulation, and – oedema reduction 	K193045 (W-2)	Jan 2020

Canada	
 – To increase blood circulation, – For the prevention of venous thrombosis – For the prevention and treatment of oedema – For promoting wound healing – For promoting healing of tendon and ligament injuries – For the treatment of venous insufficiency and ischemia 	License 86311	Jun 2011
Costa Rica	
 – For use in patients with high risk of venous thrombus-embolism and in patients in which other pharmacological and mechanical prophylaxis methods are impractical or contraindicated 	184102	Sep 2016
Ecuador	
 – To increase blood circulation, – For the prevention of venous thrombosis – For the prevention and treatment of oedema 	67680993	Jun 2017
Panama	
 – To increase blood circulation, – For the prevention of venous thrombosis – For the prevention and treatment of oedema 	8-211-2528	Aug 2016
Mexico	
 – To increase blood circulation, – For the prevention of venous thrombosis – For the prevention and treatment of oedema – For the treatment of venous insufficiency and ischemia 	2301C2017	Sep 2017

Brazil	
- To increase blood circulation,- For the prevention of venous thrombosis- For the prevention and treatment of oedema- For the treatment of venous insufficiency and ischemia-	80686360256	Dec 2019
--------	--	-------------	----------

Appendix 3: Sample Case Report Forms

Baseline (Day 0)

CASE REPORT FORM	BASELINE (DAY 0)		
STUDY SITE:	THE ROYAL STOKE UNIVERSITY HOSPITAL		
PRINCIPAL INVESTIGATOR:	[name]		
SITE NUMBER	0	2	5
PATIENT NUMBER	0		
PATIENT INITIALS			

Inclusion Criteria (All answers must be YES to include patient in study)

Male or female aged ≥ 18 years	Yes 	No 
Currently an in-patient with diagnosis of acute stroke	Yes 	No 
Use of geko™ as a mechanical prophylaxis strategy for venous thromboembolism	Yes 	No 
Patient understands and is willing to participate in the study and is able to comply with study procedures	Yes 	No 

Exclusion Criteria (All answers must be NO to include patient in study)

Pregnancy or breast feeding	Yes 	No 
Use of neuro-modulation device other than the geko™ device	Yes 	No 
Participation in any other clinical study that may interfere with the outcome of either study	Yes 	No 

Informed Consent

Has the patient freely given written informed consent?	Yes 	No 
Copy given to participant?	Yes 	No 
Date consent signed (DD/MM/YYYY)	____ / ____ / ____	

Patient Profile

Patient Age	18-30 	31-40 	41-50 	51-60 	61-70 	71-80 	Over 81 	
Gender	Male 	Female 						
Date of stroke diagnosis (DD/MM/YYYY)	____ / ____ / ____							
Current mobility - Is patient able to walk independently?	 Yes  No							
Adjunctive treatments (if any)	Drugs 	Stockings 	IPC 	None 				

DAY 0: Application of the geko™ device

Study Phase	geko™ Device Fitted	Lot Number	Expiry Date
Phase 1	geko™ T3		
Phase 2	geko™ X-T3		

CASE REPORT FORM	BASELINE (DAY 0)			DATE (DD/MM/YYYY)
STUDY SITE:	THE ROYAL STOKE UNIVERSITY HOSPITAL			
PRINCIPAL INVESTIGATOR:	[name]			

SITE NUMBER

0	2	5
---	---	---

 PATIENT NUMBER

0		
---	--	--

 PATIENT INITIALS

--	--

How easy was it to apply the geko™ device to the patients leg?

Very Easy 	Easy 	Difficult 	Very Difficult 	Impossible 
---------------------------------------	----------------------------------	---------------------------------------	--	--

If there were any difficulties, please provide a comment below:

How well did the geko™ device stick to the patients leg?

Very Well Remained attached 	Well Detached in small area 	Poorly Detached over large area 	Very Poorly Detached completely 	Not at all Would not stick at all 
--	--	--	--	--

If any level of detachment has been indicated, please provide a comment below:

Did the patient need any additional fixation to keep the geko™ device in position?

None 	Micropore Tape 	Adhesive Accessory 	OnPulse™ Knee Strap 
----------------------------------	--	--	---

If removed was the geko™ device easily re-applied?

Yes 	No 	N/A 
------------------------------	-----------------------------	------------------------------

Once applied, how comfortable for the patient was the geko™ device?

Very Comfortable 	Comfortable 	Uncomfortable 	Very Uncomfortable 	Extremely Uncomfortable 
--	---	---	--	---

If any discomfort has been indicated, please provide a comment below:

Which setting was the geko™ device set to?

1 	2 	3 	4 	5 	6 	7 	8 	9 	10 	11 
-------------------------------	-------------------------------	-------------------------------	-------------------------------	-------------------------------	-------------------------------	-------------------------------	-------------------------------	-------------------------------	--------------------------------	--------------------------------

CASE REPORT FORM	BASELINE (DAY 0)			DATE (DD/MM/YYYY)				
STUDY SITE:	THE ROYAL STOKE UNIVERSITY HOSPITAL							
PRINCIPAL INVESTIGATOR:	[name]							
SITE NUMBER	0	2	5	PATIENT NUMBER	0		PATIENT INITIALS	

Has the patient experienced any Adverse Events since signing the Informed Consent?

Yes No

If yes, please comment below:

CRF completed by:

Print Name: _____ Signature: _____ Date: ____/____/_____

To be completed by Principal Investigator:

I am confident that the information supplied in this case record form is complete and accurate data.

Signature: _____ Date: ____/____/_____

Follow-up Day 1 (please note days 1-9 CRFs will be the same)

CASE REPORT FORM		FOLLOW-UP 1 (DAY 1)			DATE (DD/MM/YYYY)	
STUDY SITE: PRINCIPAL INVESTIGATOR:		THE ROYAL STOKE UNIVERSITY HOSPITAL [name]				
SITE NUMBER		0  2  5 	PATIENT NUMBER	0   	PATIENT INITIALS	

How many hours did the patient wear the geko™ device for?					_____ hours
How well did the geko™ device stick to the patient's leg?					
Very Well Remained attached 	Well Detached in small area 	Poorly Detached over large area 	Very Poorly Detached completely 	Not at all Would not stick at all 	

If any level of detachment has been indicated, please provide a comment below:

Did the patient need any additional fixation to keep the geko™ device in position?				
None 	Micropore Tape 	Adhesive Accessory 	OnPulse™ Knee Strap 	

If removed was the geko™ device easily re-applied?				
Yes 	No 	N/A 		

If no, please comment below:

Overall, how comfortable was the geko™ device for the patient to wear?				
Very Comfortable 	Comfortable 	Uncomfortable 	Very Uncomfortable 	Extremely Uncomfortable 

If any discomfort has been indicated, please provide a comment below:

Did the patient sleep with the device on?		Yes 	No 
---	--	------------------------------	-----------------------------

DAY 1: Application of geko™ device

Current mobility - Is patient able to walk independently? (If YES is selected patient CANNOT continue in the study - please complete EXIT form)				Yes 	No 
Study Phase	geko™ Device Fitted		Lot Number	Expiry Date	
Phase 1		geko™ T3			
Phase 2		geko™ X-T3			

CASE REPORT FORM	FOLLOW-UP 1 (DAY 1)			DATE (DD/MM/YYYY)	/	/
STUDY SITE: THE ROYAL STOKE UNIVERSITY HOSPITAL	PRINCIPAL INVESTIGATOR: [name]					

SITE NUMBER

0	2	5
---	---	---

 PATIENT NUMBER

0		
---	--	--

 PATIENT INITIALS

--	--

How easy was it to apply the geko™ device to the patients leg?

Very Easy 	Easy 	Difficult 	Very Difficult 	Impossible 
---------------------------------------	----------------------------------	---------------------------------------	--	--

If there were any difficulties, please provide a comment below:

Once applied, how comfortable for the patient was the geko™ device?

Very Comfortable 	Comfortable 	Uncomfortable 	Very Uncomfortable 	Extremely Uncomfortable 
--	---	---	--	---

If any discomfort has been indicated, please provide a comment below:

Which setting was the geko™ device set to?

1 	2 	3 	4 	5 	6 	7 	8 	9 	10 	11 
-------------------------------	-------------------------------	-------------------------------	-------------------------------	-------------------------------	-------------------------------	-------------------------------	-------------------------------	-------------------------------	--------------------------------	--------------------------------

Has the patient experienced any Adverse Events since signing the Informed Consent?

Yes No

If yes, please comment below:

CRF completed by:

Print Name: _____ Signature: _____ Date: ____/____/_____

To be completed by Principal Investigator:

I am confident that the information supplied in this case record form is complete and accurate data.

Signature: _____ Date: ____/____/_____

Final Follow-up Day 10

CASE REPORT FORM	FINAL FOLLOW-UP 10 (DAY 10)			DATE (DD/MM/YYYY)	_____/_____/_____					
STUDY SITE: PRINCIPAL INVESTIGATOR:	THE ROYAL STOKE UNIVERSITY HOSPITAL [name]									
SITE NUMBER	0	2	5	PATIENT NUMBER	0			PATIENT INITIALS		

How many hours did the patient wear the geko™ device for?					_____ hours
How well did the geko™ device stick to the patient's leg?					
Very Well Remained attached 	Well Detached in small area 	Poorly Detached over large area 	Very Poorly Detached completely 	Not at all Would not stick at all 	

If any level of detachment has been indicated, please provide a comment below:

Did the patient need any additional fixation to keep the geko™ device in position?				
None 	Micropore Tape 	Adhesive Accessory 	OnPulse™ Knee Strap 	

If removed was the geko™ device easily re-applied?				
Yes 	No 	N/A 		

If no, please comment below:

Overall, how comfortable was the geko™ device for the patient to wear?				
Very Comfortable 	Comfortable 	Uncomfortable 	Very Uncomfortable 	Extremely Uncomfortable 

If any discomfort has been indicated, please provide a comment below:

Did the patient sleep with the device on?	Yes 	No 
---	------------------------------	-----------------------------

Any other comments – please add below

Day 10 final assessment and patient participation completed. Please complete Exit CRF

CASE REPORT FORM	FINAL FOLLOW-UP 10 (DAY 10)		DATE (DD/MM/YYYY)	____ / ____ / _____
STUDY SITE: PRINCIPAL INVESTIGATOR:	THE ROYAL STOKE UNIVERSITY HOSPITAL [name]			

SITE NUMBER

0	2	5
---	---	---

 PATIENT NUMBER

0		
---	--	--

 PATIENT INITIALS

--	--

CRF completed by:

Print Name: _____ Signature: _____ Date: ____ / ____ / _____

To be completed by Principal Investigator:

I am confident that the information supplied in this case record form is complete and accurate data.

Signature: _____ Date: ____ / ____ / _____

Exit Day 10

CASE REPORT FORM	EXIT			DATE (DD/MM/YYYY)	____ / ____ / ____					
STUDY SITE:	THE ROYAL STOKE UNIVERSITY HOSPITAL									
PRINCIPAL INVESTIGATOR:	[name]									
SITE NUMBER	0	2	5	PATIENT NUMBER	0			PATIENT INITIALS		
Study Exit Date (DD/MM/YYYY)	____ / ____ / ____									
Date of Last Assessment (DD/MM/YYYY)	____ / ____ / ____									
Last Assessment Completed	Baseline  Follow-up 1  Follow-up 2  Follow-up 3  Follow-up 4  Follow-up 5  Follow-up 6  Follow-up 7  Follow-up 8  Follow-up 9  Follow-up 10 									
Reason for Exit from Study	Study completed  Lost to follow-up  Non-compliance  Medical contraindication  Consent withdrawn  Other** 									
**Additional explanation required:										

CRF completed by:

Print Name: _____ Signature: _____ Date: ____ / ____ / ____

[figure not shown]
To be completed by Principal Investigator:

I am confident that the information supplied in this case record form is complete and accurate data.

[figure not shown]
Signature: _____ Date: ____ / ____ / ____

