3.2 Number of Participants

A total of 40 patients will be recruited, 20 into each phase of the study.

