4.1 Recruitment and Baseline (Day 0)

- Patient presents for geko™ therapy for VTE prevention following acute

stroke

- Confirm patient eligibility
- Obtain written informed consent
- Collect demographic data
- Fit geko™ device bilaterally for VTE prevention as per hospital standard care. The devices fitted will be as per allotted patient group and study phase.
- Record
 - Ease with which device fitted (rate from very easy to impossible)
 - Adhesion to patient's leg (rate from very well to not at all)
 - Use of additional fixation to keep the device in position
 - Ease of re-application if removed
 - Patient comfort (rate from very comfortable to extremely uncomfortable)
 - Device setting (1-11)
- Assess for any AEs

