4.2 Follow-up and Daily Application of geko™ therapy (Days 1-9)

During daily review of the patient by a member of the healthcare team, a new geko™ device will be fitted bilaterally as per standard care. In addition, the following information will be collected each day or until the patient is able to mobilize independently:

- Length of time device worn for since fitting (hours)
- Adhesion to patient's leg (rate from very well to not at all)
- Use of additional fixation to keep the device in position
- Ease of re-application if removed
- Patient comfort (rate from very comfortable to extremely uncomfortable)
- Patient sleep post-fitting
- Patient's current mobility

Fit new geko™ device bilaterally for VTE prevention as per hospital standard care. Devices fitted will be as per allotted patient group and study phase and the following post-application information recorded:

- Ease with which device fitted (rate from very easy to impossible)

- Adhesion to patient's leg (rate from very well to not at all)
- Use of any additional fixation to keep the device in position.
- Patient comfort (rate from very comfortable to extremely uncomfortable)
- Device setting (1-11)
- Assess for any AEs

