8.2 Sample Size Determination

The sample size of 20 patients per phase has been determined using MIL-STD-105, a standard commonly used in the medical device industry to specify sample size and provide the basis for acceptance and rejection. We set an acceptable quality level (AQL) of 0.15 for the function of the new formulation hydrogel and using the C=0 sampling plan (Table 2), 100% testing of 80 devices with no failures would confirm that we meet our specified AQL.

If completed on 20 patients and assuming 4 days of use (on both legs), this equates to a minimum of 80 XT-3 devices to test the new formulation the same numbers would be required for the T3 device with current hydrogel formulation for statistical comparison.

Table 2: MIL-STD-105 Statistical Sampling Plan (C=0 Sampling Plan)

MIL-STD-1916																	
Verification Level	VII		VI		V		IV		III		II		I				
INDEX VALUE																	
AQL	.010	.015	.025	.040	.065	.10	.15	.25	.40	.65	1.0	1.5	2.5	4.0	6.5	10	
LOT SIZE		SAMPLE SIZE															
2 TO 5	*	*	*	*	*	*	*	*	*	*	*	*	5	3	2	2	
9 TO 15	*	*	*	*	*	*	*	*	*	*	13	8	5	3	2	2	
16 TO 25	*	*	*	*	*	*	*	*	*	20	13	8	5	3	3	2	
26 TO 50	*	*	*	*	*	*	*	*	32	20	13	8	5	5	5	3	
51 TO 90	*	*	*	*	*	*	80	50	32	20	13	8	7	6	5	4	
91 TO 150	*	*	*	*	*	125	80	50	32	20	13	12	11	7	6	5	
151 TO 280	*	*	*	*	200	125	80	50	32	20	20	15	13	10	7	6	
281 TO 500	*	*	*	315	200	125	80	50	48	47	29	21	16	11	9	7	
501 TO 1,200	*	800	500	315	200	125	80	75	73	47	34	27	19	15	11	8	
1,201 TO 3,200	1250	800	500	315	200	125	120	116	73	53	42	35	23	18	13	9	
3,201 TO 10,000	1250	800	500	315	200	192	189	116	86	68	50	38	29	22	15	9	
10,001 TO 35,000	1250	800	500	315	300	294	189	135	108	77	60	46	35	29	15	9	
35,001 TO 150,000	1250	800	500	400	4776	294	218	170	123	96	74	56	40	29	15	9	
150,001 TO 500,000	1250	800	750	715	476	345	270	200	156	119	90	64	40	29	15	9	
500,001 AND OVER	1250	1200	1112	715	536	435	303	244	189	143	102	64	40	29	15	9	

* Indicates entire Lot must be inspected 100%. **Note:** Acceptance number in all cases is zero.

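### Two devices are worn each day, but the sample CRFs take one adhesion score per patient-day with no left/right field and no stated rule for which leg to rate

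*Combined protocol and SAP*

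**What the plan says.** - **Fitting.** Section 4.1 (Day 0) instructs: "Fit geko™ device bilaterally for VTE prevention as per hospital standard care". Section 4.2 says that at each daily review on Days 1-9 "a new geko™ device will be fitted bilaterally as per standard care". Two devices are therefore in use on each patient-day.
- **Unit of the acceptance rule.** Section 8.2 sets the criterion per device: "100% testing of 80 devices with no failures would confirm that we meet our specified AQL". It obtains the number of devices by "assuming 4 days of use (on both legs), this equates to a minimum of 80 XT-3 devices".
- **Primary analysis.** Section 8.1 scores adhesion numerically and compares the cohorts with an unpaired t-test for equivalence. It does not say whether the unit is the device, the leg, the day or the patient.
- **Forms (Appendix 3).** The Days 1-9 and Day 10 forms ask "How well did the geko™ device stick to the patient's leg" once, with five categories, and "How many hours did the patient wear the geko™ device for" once. The Day 0 form has one adhesion row and no hours field. Additional fixation and re-application have one row each on all forms. Device setting and lot number appear on the Day 0 to Day 9 forms only, with one setting row and one lot-number line per study phase. No form identifies a leg.
- **Leg rule.** Sections 4.1 to 4.3 and 7.4 also speak of the patient's leg in the singular. No section says which leg to rate when the two differ.

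**The concern.** If one device stays on and the other comes off, the person completing the form must choose one category for two different results. The choice may be the worse leg, the better leg or an overall impression, and the recorded value does not show which.

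Two things are at stake. The first is the primary score, because the same pair of devices can be scored differently by different staff. The second is the zero-failure criterion in Section 8.2, which needs a result for each device while the form holds one result for two.

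The design makes this worse. Section 3.0 describes a non-blinded, non-randomised study in which Group 1 finishes before Group 2 is consented. If the ward's rating habit shifted between phases, the shift would coincide exactly with the change of hydrogel, and the data could not separate the two.

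**Working it through.** **Step 1: the plan's own figure.** Table 2 in Section 8.2 gives a sample of 80 in its .15 column for lot sizes from 51 to 1,200, so the table lookup reproduces. The device count does not. The inputs are 20 patients per phase (Section 3.2), 4 days and both legs (Section 8.2):

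- 20 × 4 × 2 = 160 devices
- 20 × 4 = 80 patient-days

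The stated 80 equals the number of patient-days, which is also the number of end-of-wear adhesion ticks. The plan calls 80 a minimum, so 160 devices would not be a shortfall. The point is that 80 ticks would stand for 160 devices. If only 80 devices were fitted bilaterally, they would yield 40 ticks. With fittings on Days 0 to 9 and no early exit, a phase would use 20 × 10 × 2 = 400 devices and record 20 × 10 = 200 end-of-wear ticks.

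**Step 2: what the ticks reveal about device failures.** Suppose k of 80 ticks show failure. The number of failed devices among 160 is then:

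| Rating convention | Range | k = 0 | k = 4 |
|---|---|---|---|
| Worse leg | k to 2k | 0 | 4 to 8 |
| One unspecified leg | k to 80 + k | 0 to 80 | 4 to 84 |
| Better leg | 2k to 80 + k | 0 to 80 | 8 to 84 |

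Only under worse-leg rating does zero failing ticks mean zero failed devices.

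**Step 3: recorded failure rate.** The documents give no detachment rate or between-leg correlation, so these are assumptions. Let p be the chance that a device detaches and r the correlation between the two legs of a patient on one day.

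- Both legs fail (recorded under better-leg rating): p² + r·p(1−p)
- At least one fails (recorded under worse-leg rating): 2p − [p² + r·p(1−p)]
- Legs differ: 2p(1−p)(1−r)

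For p = 0.05 and r = 0.5: both fail = 0.0025 + 0.5 × 0.0475 = 0.02625; at least one fails = 0.10 − 0.02625 = 0.07375; legs differ = 0.095 × 0.5 = 0.0475.

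| p | r | Legs differ | Worse leg | Better leg |
|---|---|---|---|---|
| 5% | 0 | 9.5% | 9.75% | 0.25% |
| 5% | 0.5 | 4.75% | 7.4% | 2.6% |
| 2% | 0 | 3.92% | 3.96% | 0.04% |
| 2% | 0.5 | 1.96% | 3.0% | 1.0% |

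At p = 5%, the legs would differ on about 7.6 of 80 patient-days if independent (80 × 0.095) and 3.8 at r = 0.5 (80 × 0.0475).

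**Step 4: chance of recording no failure in 80 patient-days.** This is (1 − recorded rate)^80, taking patient-days as independent.

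| p | r | Worse leg | Better leg |
|---|---|---|---|
| 5% | 0 | 0.0003 | 0.82 |
| 5% | 0.5 | 0.002 | 0.12 |
| 2% | 0 | 0.04 | 0.97 |
| 2% | 0.5 | 0.09 | 0.44 |

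Correlation narrows the gap. It closes only if the two legs always agree.

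**The case against.** The strongest reply is that the primary endpoint is a comparison of patient cohorts and no section makes the device its unit. One score per patient-day can feed that comparison, and the zero-failure count appears only in the sample-size rationale, not in Section 8.4. This stands in part. A reader might infer that the primary outcome is undefined whenever the legs differ, but the documents support only that it is ambiguous. Section 10.0 says that CRF completion guidelines go to the site, the forms are headed as samples, and a leg rule may exist there.

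A reader might also infer that the zero-failure decision is always lost. It is not: a worse-leg rule would preserve the yes/no decision, though not the number of failures or the device-level scores.

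The forms request a comment when detachment is ticked, and Section 13.1 makes the medical record the primary source. Some discordant days might be recovered that way. But the comment does not ask for the leg, and a better-leg tick in the top category triggers no comment at all.

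The sizes above depend on assumed rates. The legs of one patient share skin, position and fitter, so independence is an extreme case. The worse-leg versus better-leg contrast also assumes that every rater follows the same extreme. Early exits on regaining mobility would reduce the number of intervals.

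Finally, a reader might expect unequal legs because these are stroke patients. The documents say only that patients are immobile and bedbound, and nothing links leg weakness to adhesion. The point does not need that argument.

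**Conclusion.** The point holds for the structured fields: two devices per patient-day, one adhesion tick and one fixation tick on every daily form, one wear time on Days 1-10, and no leg identifier or leg rule in the documents shown. On days when the legs differ, the score of at least one device is not recorded as such, and the number of device failures cannot be derived from those fields.

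The documents do not fix how much this matters. In the range examined (detachment of 2% or 5%, between-leg correlation of 0 or 0.5), the rating convention alone changes the recorded failure rate by 2 to 9.5 percentage points, which is the share of days on which the legs differ. A change of convention between phases could produce or hide a difference between the gels. There is no evidence that such a change would occur, only that the design could not detect it.

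The related discrepancy in Section 8.2 (160 devices from its own inputs, 80 stated) should be settled at the same time, since 80 is the number of patient-days.

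**What to change.** Before the first patient is enrolled:

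1. Split into Left and Right the device-level rows that each form already has: adhesion, fixation and re-application on all forms; hours worn on Days 1-10; setting and lot number on Days 0-9.
2. State which adhesion categories count as a failure. The five-point scale is not mapped to failure anywhere, so the count would remain undefined even with per-leg rows.
3. In Section 8.2, count failures per device from the per-leg rows, and correct the device arithmetic.
4. In Section 8.1, average the two legs within patient-day and then the days within patient, so that the t-test compares one value per patient.

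The cost is a CRF revision and slightly longer form completion. Both devices are already replaced at the daily review, so no extra visit, procedure or staff is needed. A written worse-leg rule in the completion guidelines would be cheaper, but would protect only the yes/no zero-failure decision.
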